**Statistical Analysis Plan**

Catalyst Biosciences, Inc. Protocol # MAA-201

Version 2.0

Syneos Health #1009647

calculated as (cumulative number of bleeding days recorded in bleed history / 180). The proportion of bleeding days post-treatment will be calculated as (cumulative number of bleeding days from the first SC dose to last dose in eDiary in Part 2 / cumulative number of actual treatment days for each dose level in Part 2). The analysis will be performed using ITT, modified ITT and per-protocol population.

Graphic presentation will also be provided for the interval of each bleeding event and each subject.

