## 8. EFFICACY

Efficacy analyses will be based on the ITT, modified ITT and per-protocol population and summarized by study part, final dose level and overall.

The primary efficacy endpoint will be tested inferentially using a one-sided test with 2.5% significance level. All other statistical tests will be performed at the 0.05 significance level using two-sided tests (i.e. two-sided 95% CIs).

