## 8.2 SECONDARY ENDPOINTS AND ANALYSES

### 8.2.1 Analysis of Occurrence of Breakthrough Bleeds and Proportion of Bleeding Days

A breakthrough bleed is any spontaneous or traumatic bleed. Subjects who had breakthrough bleeds out of total bleedings will be summarized separately as spontaneous and traumatic as well as combined and listed using ITT, modified ITT population and per-protocol population.

Breakthrough bleeding events will be categorized and summarized as follows:

- Number and percentage of bleeds that are life threatening for each dose level within each study part
- Number and percentage that require hospitalization and/or blood transfusion for each dose level within each study part
- Number and percentage of muscle bleeds for each dose level within each study part

A listing of breakthrough bleeding events will be provided, including start and end date of bleeding.

Mean pre-treatment between bleeding intervals for all subjects will be compared with post-treatment between bleeding intervals for each dose level in Part 2 using paired t-test. This analysis will only be performed if there are at least 6 data points at pre- or post treatment. The analysis will be performed using ITT, modified ITT and per-protocol population.

The proportion of bleeding days pre-treatment by subject will be compared with the proportion of bleeding days post-treatment for each dose level in Part 2 using paired t-test after transforming the individual proportions by an arcsin transformation ( $2 \cdot \arcsin(\sqrt{p})$ ). This analysis will only be performed if there are at least 6 data points at pre- or post treatment. The proportion of bleeding days pre-treatment will be

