### 12.1 EXTENT OF EXPOSURE

Exposure to study drug (in days) will be calculated for part 2 for each dose level and overall for all dose levels.

Exposure is calculated as below:

Exposure in part 2 for each dose level = cumulative number of actual treatment days for each dose level

Exposure overall in part 2 = cumulative number of actual treatment days of the dosing

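### The post-treatment proportion of bleeding days in SAP 8.2.1 divides bleeding over all of Part 2 by the treatment days of one dose level, which distorts the value for escalated subjects and can push it above 1.

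*SAP*

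**What the plan says.** SAP 8.2.1 sets the pre-treatment proportion against the "proportion of bleeding days post-treatment for each dose level in Part 2" by paired t-test, "after transforming the individual proportions by an arcsin transformation", that is 2·arcsin(√p). By SAP 8 this test is two-sided at 0.05.

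- Pre-treatment proportion: "cumulative number of bleeding days recorded in bleed history / 180". Numerator and denominator are meant to cover the same six-month history.
- Post-treatment numerator: "cumulative number of bleeding days from the first SC dose to last dose in eDiary in Part 2".
- Post-treatment denominator: "cumulative number of actual treatment days for each dose level in Part 2".

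SAP 12.1 settles what the denominator means. It defines per-level exposure in the same words ("Exposure in part 2 for each dose level = cumulative number of actual treatment days for each dose level") and words whole-period exposure differently ("Exposure overall in part 2 = cumulative number of actual treatment days of the dosing"). SAP 8.2.1 uses the per-level wording. Neither SAP 8.2.1 nor SAP 14 (changes from the protocol) limits the numerator to a level or provides for a proportion above 1.

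**The concern.** The numerator has its own start and end, which span Part 2. The denominator spans one level. A programmer who follows the text will charge a bleed at 30 µg/kg to the 60, 90 and 120 µg/kg values as well, and later bleeds back to 30 µg/kg. The comparator has no such mismatch, so the paired difference mixes a drug effect with an artefact of escalation. Where Part 2 bleeding days outnumber treatment days at a level, p exceeds 1 and the transform has no real value. SAP 6.2 does not impute missing data, so those values would drop out, and they belong to the subjects who escalated fastest.

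**Working it through.** **Range of paths.** Protocol 1.1 gives up to 197 days of daily dosing in Part 2. This is reproduced by three lower levels of 49 days plus 50 days at the fourth: 3 × 49 + 50 = 197. Escalation can follow a spontaneous bleed after the fifth daily dose, up to three times (SAP 3.6), so a stay of about 6 days at a lower level is possible.

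**Formulas.** Let b_j be the bleeding days and T_j the treatment days at level j, and let B be the sum of the b_j.
- As written: p_j = B / T_j.
- Matched: p_j = b_j / T_j.
- Inflation: B / b_j. If bleeding is equally likely on every day, this equals (sum of T_j) / T_j.

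**Inflation with equal daily bleeding**
- No escalation: 50/50 = 1.0.
- 6 then 50 days: 56/6 = 9.3 and 56/50 = 1.12.
- 25 then 50 days: 75/25 = 3.0 and 75/50 = 1.5.
- 49/49/49/50 days: 197/49 = 4.0 and 197/50 = 3.9.

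**Specific paths, one escalating bleed per lower level and none at the last**

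| Days per level | Bleed length | As written | Matched |
|---|---|---|---|
| 49/50 | 2 days | 2/49 = 0.041; 2/50 = 0.040 | 0.041; 0 |
| 49/49/49/50 | 3 days | 9/49 = 0.184 (three times); 9/50 = 0.18 | 3/49 = 0.061 (three times); 0 |
| 6/6/6/50 | 3 days | 9/6 = 1.50 (three times); 9/50 = 0.18 | 3/6 = 0.50 (three times); 0 |
| 6/6/50 | 5 days | 10/6 = 1.67 (twice); 10/50 = 0.20 | 5/6 = 0.83 (twice); 0 |

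The values 1.50 and 1.67 cannot be transformed.

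**Average size.** This needs a bleed length, which the documents do not give. Assumptions: every bleed lasts 2 days and counts as spontaneous, the bleeding rate is constant, the first bleed after the fifth dose ends a lower level, and a level otherwise ends at 50 days. The pre-treatment proportion at ABR 12 is 12 × 2 / 365 = 0.066. Simulated means are over subjects who reach each level.

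| | On-treatment ABR 12 (no effect) | On-treatment ABR 6 (halved) |
|---|---|---|
| As written, 30/60/90/120 µg/kg | 0.38/0.46/0.54/0.21 | 0.13/0.22/0.28/0.16 |
| Subjects with any value above 1 | about 19% | about 2.6% |

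Repeat runs at ABR 12 gave 0.37–0.38, 0.44–0.46, 0.51–0.54 and 0.20–0.21, with 18–19% above 1. That share is about 1.5% with 1-day bleeds and 32% with 3-day bleeds.

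**What matching does and does not repair.** At 120 µg/kg, which no bleed can end, the matched mean is 0.066 at ABR 12 and 0.033 at ABR 6, both correct. At the lower levels it stays near 0.116 against 0.066 with no drug effect, because those levels end at a bleed. Matched values can also exceed 1 if Day 0 bleeding days (Protocol 8.2.6) enter the numerator but not the treatment days. This affected 0–30% of escalated subjects over ABR 3–24 and mean bleed lengths of 1–5 days.

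**The case against.** **The level could be read into both parts.** SAP 8.2.1 frames the comparison by dose level and the phrase closes the ratio, so a sympathetic programmer might limit the numerator too. That may be the intention, but the numerator carries an explicit window and nothing in the text overrides it. The wording needs correcting either way.

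**Overstatement.** A reader might infer that every escalated subject will show more bleeding on drug whatever the drug does, or that inflation is always several-fold. The documents support neither. The 49/50-day path gives 0.041 and 0.040, both below 0.066. At ABR 6 with 2-day bleeds, about 39% of escalated subjects have a final-level value below 0.066. The means are also pulled up by short stays: the median at 30 µg/kg at ABR 6 is 0.047, below the pre-treatment value. These means are untransformed, whereas the test uses the arcsine scale.

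**Replacing the per-level tests.** One might conclude that a single whole-Part-2 proportion should take their place. It has its own bias, in the drug's favour, because subjects at the first three levels finish after 50 days without spontaneous bleeding (Protocol 4.2): about 0.057 against 0.066 with no drug effect. Dropping the per-level tests is a trade-off that the mismatch does not force.

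**Low stakes.** This stands. The proportion of bleeding days is not among the endpoints in SAP 4.2, and listings of bleed dates would let an odd value be traced and corrected.

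**Conclusion.** The definition is wrong as written for subjects who escalate. Subjects who never escalate are unaffected. After one escalating bleed and no later bleed, the lower level is right and the final level shows a positive value instead of 0. With short stays or several escalations the inflation is several-fold, and p can pass 1 within the protocol's own rules. Under the 2-day assumption, an ineffective drug would on average look far worse than no treatment, and a drug that halves bleeding could still appear on average to worsen it. The path arithmetic needs only stays and bleed lengths that the protocol allows. The averages rest on the assumed bleed length and constant rate. This is a supportive secondary analysis and should be corrected before database lock; the primary ABR test and the sample size do not use it.

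**What to change.** In SAP 8.2.1, redefine the post-treatment proportion:

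1. For each level, count in the numerator only bleeding days at that level, each calendar day once.
2. Count Day 0 days and interrupted days in both numerator and denominator or in neither, and say which, so that p cannot exceed 1.
3. Start the window at the first Part 2 dose, since the first SC dose is given in Part 1b.
4. State that matched values at levels left because of a bleed remain biased upward (about 0.116 against 0.066 in the no-effect case above), so tests at those levels need cautious interpretation.
5. Optionally add, as supportive, one proportion per subject over all of Part 2 (Part 2 bleeding days / Part 2 days), with the note that early completion biases it slightly in the drug's favour.

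The cost is a few sentences in the SAP and a small change to the derivation program. No new data are needed: the diary already records bleed onset, bleed resolution and injection dates (Protocol 8.1 and 8.2.4).

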### 8.2.2 Analysis of Occurrence of Clinical Thrombotic Event

The following categories will be summarized using ITT and modified ITT population:

- the number and percentage of subjects with thrombotic event (1 or more events)
- the number and percentage of subjects with one thrombotic event
- the number and percentage of subjects with two thrombotic events
- the number and percentage of subjects with three thrombotic events

The data will be listed.

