### 4.2 SECONDARY ENDPOINTS

The secondary endpoints will include:

- Occurrence of breakthrough bleeds requiring escalation to higher dose level.
- Safety parameters: Occurrence of clinical thrombotic event not attributable to another cause, and occurrence of antibody formation resulting in a decreased endogenous level of FVII or FVIIa.
- Change in coagulation parameters (prothrombin time (PT), activated partial thromboplastin time (aPTT), fibrinogen, MarzAA antigen and activity levels, and thrombin generation test (TGT)) from pre-dose.
- Occurrence of an antibody response to MarzAA and whether it is inhibitory and cross-reactive to wt-rFVIIa or wt-FVII.
- Clinically significant levels of thrombogenicity markers resulting from daily SC administration of MarzAA
- Feasibility and ease of use of daily SC self-administration by patient as measured by compliance with treatment
- Breakthrough bleeding events will be categorized as follows:
  - Number of bleeds that are life threatening
  - Number that require hospitalization and/or blood transfusion
  - Number of muscle bleeds

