### 5.2 SAFETY POPULATION

Safety population is defined as any patient who receives at least one dose.

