### 5.3 INTENT-TO-TREAT (ITT) POPULATION

ITT population is defined as any patient who receives at least one dose.

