### 5.4 MODIFIED ITT POPULATION

Modified ITT population is defined as any patient who receives at least 7 SC doses at 30 µg/kg.

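### The thrombotic-event table in SAP 8.2.2 inherits grouping by final dose and is repeated in the modified ITT set, so its by-dose denominators are wrong once anyone escalates and its modified ITT rate can omit an early event

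*SAP*

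**What the plan says.** SAP 4.2 lists the endpoint as a safety matter: "Safety parameters: Occurrence of clinical thrombotic event not attributable to another cause". Its analysis nevertheless sits in SAP Section 8 (Efficacy), at 8.2.2, which states: "The following categories will be summarized using ITT and modified ITT population". The categories that follow count subjects with any, one, two or three events. No dose grouping is given, and a listing is promised.

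The lead of Section 8 sets the default: "Efficacy analyses will be based on the ITT, modified ITT and per-protocol population and summarized by study part, final dose level and overall". SAP 8.2.1 departs from that default for categories of bleed, for example "Number and percentage of muscle bleeds for each dose level within each study part". SAP 8.2.2 contains no such departure.

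The population definitions are:
- SAP 5.2: "Safety population is defined as any patient who receives at least one dose".
- SAP 5.3: "ITT population is defined as any patient who receives at least one dose".
- SAP 5.4: "Modified ITT population is defined as any patient who receives at least 7 SC doses at 30 µg/kg".

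Up to three escalations within a subject are possible (SAP 3.6). Protocol 6.1.2.3 includes a thrombotic event among the reasons for interrupting injections. Protocol 7.2 and SAP 3.5 require a subject who does not complete to be replaced.

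**The concern.** Two features of 8.2.2 do not suit a harm endpoint in this design.

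First, in a trial where one subject may pass through several doses, the final dose describes where he ended. It need not be the dose he was on when the event occurred, and it does not show who was exposed to each dose. Risk by dose needs the number exposed at that dose as its denominator.

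Second, membership of the modified ITT set depends on what happens after treatment starts. An early thrombosis that stops dosing can itself keep the subject out of the set, so the set is partly selected on the outcome being counted.

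Thromboembolic events are one of the two adverse events of special interest in Protocol 8.5.7. At stake is whether the one table dedicated to them can be read by dose, and whether its modified ITT version can show no events when one occurred.

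**Working it through.** The documents give no expected thrombotic rate, so there is no planned figure to reproduce. The counts below are assumed for illustration. The planned 12 subjects come from SAP 3.5. Each rate is x/n, and the intervals are exact (Clopper-Pearson) 95%.

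**Step 1: which grouping applies.** SAP 8.2.2 sets its own populations but no dose grouping. The Section 8 lead supplies final dose level. SAP 8.2.1 replaces that rule for its bleed categories and 8.2.2 does not. Followed as written, the thrombotic table is grouped by final dose.

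**Step 2: effect of final-dose grouping.** Assume all 12 start daily dosing at 30 µg/kg and 4 later escalate to 60. Final-dose denominators are 12 − 4 = 8 at 30 and 4 at 60. Subjects actually exposed number 12 at 30 and 4 at 60. Place one event at 30.

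| Case | Level | By final dose | By dose at onset |
|---|---|---|---|
| A: event ends treatment | 30 | 1/8 = 12.5% (0.3 to 52.7) | 1/12 = 8.3% (0.2 to 38.5) |
| A | 60 | 0/4 | 0/4 |
| B: subject resumes, later escalates | 30 | 0/8 = 0% (0 to 36.9) | 1/12 = 8.3% (0.2 to 38.5) |
| B | 60 | 1/4 = 25.0% (0.6 to 80.6) | 0/4 = 0% (0 to 60.2) |

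In case A the event is at the right dose, but the denominator omits 4 exposed subjects. In case B the event itself is also at the wrong dose. The denominator error arises whenever anyone escalates. The numerator error needs a change of level after the event.

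**Step 3: effect of the modified ITT set.** Assume one subject has an event before his seventh SC dose at 30 µg/kg and stops, and all others reach seven.
- Without replacement: ITT 1/12 = 8.3% (0.2 to 38.5); modified ITT 0/(12 − 1) = 0/11 = 0% (0 to 28.5).
- With the replacement rule: ITT 1/(12 + 1) = 1/13 = 7.7% (0.2 to 36.0); modified ITT 0/(13 − 1) = 0/12 = 0% (0 to 26.5).

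Replacement restores the modified ITT denominator to 12, so that table can look complete and free of events.

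**Step 4: whether another table covers the gap.** SAP 12.3 tabulates treatment-emergent events in the safety population by Part 2 dose level. Two things limit it as a substitute. Rows are by system organ class and preferred term with no thrombotic or special-interest grouping, so the events named in Protocol 8.5.7 would be spread over several terms. Its assignment rule also gives a start for each dose level but no end, so an event that begins on 60 also satisfies the rule for 30.

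**The case against.** The strongest reply is that little is hidden. ITT and safety have the same definition, so naming the safety population in 8.2.2 changes no subject and no count. An early event stays in the ITT table, in the overall row and in the listing. SAP 12.3 also gives treatment-emergent events by dose level. All of that stands. A reader might infer that an early thrombosis disappears from the report; the documents do not support that. Only the parallel modified ITT summary loses it.

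A reader might also infer that 8.2.2 charges events to doses the subjects were not on. It does not say so itself. The grouping comes from a sentence about efficacy analyses, and whether that sentence was meant to reach an endpoint labelled as safety can be disputed. Even where it applies, an event that ends Part 2 treatment has its onset dose as its final dose. The wrong-dose error and the loss through early stopping are therefore different scenarios and cannot both befall one event. Restart after interruption is foreseen (Protocol 8.5.3.3), so the wrong-dose case is possible. De-escalation is described as not expected (Protocol 6.1.2.2).

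Finally, escalation is triggered by bleeding, and one stated aim of Part 2 is safety at each subject's optimal dose (Protocol 4.1). A final-dose view has some use for that aim. The documents do not say that the design must establish a relation between dose and thrombosis. What the reply leaves untouched is the denominator error, the outcome-dependent modified ITT set, and the lack of any planned thrombotic table by dose at onset.

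**Conclusion.** The point holds in a limited form. Read with the Section 8 lead, 8.2.2 gives by-dose thrombotic rates whose lower-dose denominators omit escalated subjects: 1/8 instead of 1/12 in the illustration. It puts an event at the wrong dose only when the subject resumes and later changes level. The modified ITT run is biased downward when an early event stops treatment, for example 0/12 against 1/13 in ITT after replacement.

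The sizes rest on assumed counts: one event, and 4 of 12 subjects escalating to 60. With so few subjects the exact intervals are wide and overlap heavily, so the matter is correct display and not a change in any test. The overall ITT incidence is sound. The SAP should be corrected because the by-dose and modified ITT summaries would otherwise be misread, and SAP 12.3 does not fully replace them.

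**What to change.** The change is to the analysis only. Rewrite SAP 8.2.2 so that:
- thrombotic events are summarised in the safety population, by study part and dose level at onset, with an overall row;
- the denominators at each level are the subjects exposed to it and, in Part 2, the exposure days at it, which SAP 12.1 already derives;
- the modified ITT run is dropped for this endpoint or marked as supportive.

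Exact confidence intervals are optional, since SAP Section 12 plans descriptive safety summaries only. The cost is a few lines of SAP text and one table replaced by another from the same data. No new data are needed and trial conduct is unaffected.

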### 8.2.3 Analysis of Coagulation

Actual and change from baseline values will be summarized for the following coagulation parameters:

- PT
- aPTT
- fibrinogen
- MarzAA antigen activity level
- TGT

## 8.3 EXPLORATORY ENDPOINTS AND ANALYSES

### 8.3.1 Analysis of European Quality of Life-5 Dimensions (EQ-5D)

The EQ-5D descriptive system comprises the following 5 dimensions: mobility, self-care, usual activities, pain/discomfort and anxiety/depression. Each dimension has 5 levels: no problems, slight problems, moderate problems, severe problems and unable to

**Statistical Analysis Plan**

Catalyst Biosciences, Inc. Protocol # MAA-201

**Version 2.0**

**Syneos Health #1009647**

perform. Score 1, 2, 3, 4 and 5 will be assigned to each level: level 1 = 1, level 2 = 2, level 3=3, level 4=4 and level 5=5.

The health state index score will be calculated based on EQ-5D-5L Index Value Calculator - EuroQol, assessing the dimension scores from the 5 dimensions using the UK version, ranging between 1.0 (best imaginable health) and -0.594 (worst imaginable health).

Descriptive analysis for actual and change from baseline scores for health state index score will be provided by study part, dose level and visit.

The one sample Wilcoxon signed rank test for a single group will be used to compare the baseline health state index score vs. the last post-baseline assessment at the final treatment dose health state index score, independently for each dose level in Part 2. A 95% Confidence interval for the median change from baseline value at the last post-baseline assessment at the final treatment dose will also be obtained. Sample SAS code can be found in Appendix I.

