### 3.5 DETERMINATION OF SAMPLE SIZE

With a total of 12 subjects and assuming a null hypothesis of an ABR of 12, then if the true ABR for MarzAA is 6 or less, with a one-tailed 2.5% significance level there is near 100% power to demonstrate this using a one sample Poisson test of the null hypothesis. Even if only 6 subjects were available to be pooled for this analysis, the power would still be in excess of 99%. Thus, a sample of 12 subjects is expected to provide sufficient power for the primary endpoint analysis in this study.

Twelve subjects were chosen to increase the size of the safety data set.

If a subject does not complete the study as defined in the protocol (i.e., before receiving study drug for 50 days at the same dose level) another subject will need to be enrolled in replacement.

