#### Part 2: Daily SC administration

At Day 1 of daily SC dosing, subjects will begin their self-administered dosing regimen. MarzAA will be self-administered by subjects daily (at approximately the same time every day), starting with a SC dose of 30 µg/kg MarzAA. At each dose, subjects will record the day and time of the SC injections in their diary. If a spontaneous bleeding episode (defined as one that is precipitated by normal activities of daily living [ADL]) occurs before the fifth daily dose, subjects will continue at the current dosing level. If a spontaneous bleeding episode occurs after the fifth daily dose, the MarzAA dose will be escalated to the next dose level. Three dose escalations are allowed during part 2: 60, 90, and 120 µg/kg (maximum dose). At each dose level escalation, safety and PK/PD will be monitored to ensure that dose escalation to a higher dose level is appropriate. If a subject requires a third dose escalation to the fourth dose level, then they will continue treatment with that dose for 50 days and complete the study, regardless if a spontaneous bleeding episode occurs during the highest treatment dose level.

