### **8.3.3 Analysis of Hemophilia A quality of life questionnaire (Haem-A-QoL)**

Haem-A-QoL comprises of 10 scales and one total Haem-A-QOL transformed score (HAEMA\_Z):

- Physical health (PHYS) - 5 items
- Feelings (FEEL) - 4 items
- View of yourself (VIEW) - 5 items
- Sports and Leisure (SPORT) - 5 items
- Work and school (WORK) - 4 items
- Dealing with Haemophilia (DEAL) - 3 items
- Treatment (TREAT) - 8 items
- Future (FUTURE) - 5 items
- Family planning (FAMPL) - 4 items
- Partnership and sexuality (SEXUAL) - 3 items

Statistical Analysis Plan

Catalyst Biosciences, Inc. Protocol # MAA-201

Version 2.0

Syneos Health #1009647

For the detailed scoring method, please see [Appendix III](#).

Descriptive analyses for the actual and change from baseline scores for Haem-A-QoL will be provided for each of the dimensions by study part, dose level and visit.

The one sample Wilcoxon signed rank test for a single group will be used to compare the baseline Haem-A-QoL result vs. the last post-baseline assessment at the final treatment dose Haem-A-QoL result per subject, independently for each dose level in Part 2. A 95% Confidence interval for the median change from baseline value at the last post-baseline assessment at the final treatment dose will also be obtained. Sample SAS code can be found in Appendix I.

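### The signed-rank tests on patient-reported outcomes are split by final dose level, where five or fewer subjects can give neither p < 0.05 nor a 95% median interval; the SAP should specify one pooled test.

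*SAP*

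**What the plan says.** SAP 8.3.1 (EQ-5D) sets the test: "The one sample Wilcoxon signed rank test for a single group will be used to compare the baseline health state index score" against "the last post-baseline assessment at the final treatment dose health state index score, independently for each dose level in Part 2". Sections 8.3.2 (VAS) and 8.3.4 (HAL) use the same rule, again "independently for each dose level in Part 2", and 8.3.3 applies it to the "Haem-A-QoL result per subject, independently for each dose level in Part 2". SAP Section 8 sets the level: "All other statistical tests will be performed at the 0.05 significance level using two-sided tests".

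The planned number is 12 (SAP 3.5), and there are four possible final levels: the starting level plus the escalations in SAP 3.6, "Three dose escalations are allowed during part 2: 60, 90, and 120". Missing data are not imputed (SAP 6.2).

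Three places bear on whether anything is pooled:
- The interval sentence promises "A 95% Confidence interval for the median change from baseline value at the last post-baseline assessment at the final treatment dose" but does not repeat the dose-level phrase.
- The Appendix I sample code for the test and interval is a `proc univariate` call with the distribution-free option `cipctldf`. It has no BY, CLASS or WHERE statement for dose.
- The opening of Section 8 says efficacy results are summarized by study part, by final dose level and overall.

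**The concern.** A subject has one final dose, so tests at the final dose run separately by level use disjoint subsets of the 12 subjects. The exact signed-rank test and the order-statistic interval both have a hard floor on sample size. Below it, no data, however favourable, can give a significant result or an interval with 95% coverage. A non-significant p-value from three subjects would carry almost no information, yet could be read as absence of benefit.

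The SAP guards against this elsewhere. It requires at least six data points, subjects or observations for the paired t-tests in 8.2.1, dose proportionality in 9.5, the comparison of PD data with baseline in 10.4 and the bleeding-group models in 10.5. Section 8.3 has no such rule.

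**Working it through.** **The plan's own figure.** The documents give no power, sample size or minimum n for the patient-reported outcomes. The only justification for 12 subjects concerns the primary Poisson test: "With a total of 12 subjects and assuming a null hypothesis of an ABR of 12", against a true rate of 6 or less, one-sided 2.5%. With one subject-year each, as the SAP 8.1.1 formula implies:
- 12 subjects: mean count 144 versus 72, critical count 120, attained level 0.0227, power above 0.9999.
- 6 subjects: mean count 72 versus 36, critical count 55, attained level 0.0224, power 0.9988.

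Both statements reproduce on that footing. They say nothing about the tests in 8.3.

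**Floor for one level.** With n non-zero, untied changes all in one direction, the smallest two-sided exact signed-rank p is 2/2^n. The widest order-statistic interval for the median (minimum to maximum) covers 1 − 2/2^n.

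| n | Smallest p | Widest coverage |
|---|---|---|
| 3 | 0.25 | 75% |
| 4 | 0.125 | 87.5% |
| 5 | 0.0625 | 93.75% |
| 6 | 0.03125 | 96.9% |
| 12 | 0.0005 | 99.95% |

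Six is the threshold for both. Zero changes drop out of the signed-rank test, so six subjects are necessary for the test but may not be enough.

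**Splitting 12 over four levels.** There are 455 ordered splits. In 125 no level has six, in 324 exactly one does, and in 6 (the 6/6 splits) two do. At least two of the four levels therefore always fall below six. Some of those may be empty.

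**How likely a poor split is.** The documents give no distribution of final dose, so this is an illustration. Assumptions: a constant spontaneous bleed rate, the same at all four levels; 45 at-risk days per level (50 days less the first five doses, before which a bleed does not trigger escalation); 12 independent subjects with complete data. Then q = exp(−ABR × 45/365) is the probability of finishing at a given level without escalation. The final-level probabilities are q, q(1−q), q(1−q)² and (1−q)³, and the counts are multinomial. At ABR 6, q = exp(−0.740) = 0.477 and the expected numbers are 5.7, 3.0, 1.6 and 1.7.

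| Spontaneous ABR | Chance no level reaches 6 | Mean share of subjects in levels below 6 |
|---|---|---|
| 12 | 45% | 68% |
| 6 | 39% | 65% |
| 4 | 10% | 42% |
| 3 | 3% | 31% |
| 1 | about 0 | 12% |

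At ABR 1, 10.6 of 12 subjects are expected to stay at the first level.

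**The case against.** Four points can be made for the plan.

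**Pooling may be intended.** The interval sentence omits the dose-level phrase, the sample code has no dose split, and Section 8 promises an overall summary. Run on one dataset of final-dose changes, the code would give one pooled test and one pooled interval. This stands as far as it goes: a reader might infer that all pooling is excluded, and the documents do not support that. But the code is only an example, a summary is not a test, and the four sentences that define the test all say it is run by level.

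**The scale depends on weak efficacy.** SAP 3.5 plans for a rate of 6 or less, so 6 is the edge of that range. The illustration also assumes no dose response, and only spontaneous bleeds trigger escalation, so a total rate of 6 would mean fewer escalations. This stands. It is tempting to say that the tests fail in most levels, but that counts empty levels, where nothing is lost. At ABR 1, most occupied levels fail in only 11% of trials.

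**The endpoints are exploratory.** Descriptive changes are planned by part, dose level and visit, and no primary or secondary conclusion rests on these p-values. A reader might infer that the quality-of-life question cannot be answered; that is too strong.

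**Pooling mixes doses from 30 to 120 µg/kg.** True, and a real if small cost. But the SAP's own contrast is baseline versus each subject's final dose, and the protocol's aim in Part 2 is to find each subject's own dose (protocol 4.1).

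**Conclusion.** The point holds as a limited, cheaply repaired weakness. As written, the test is run within final dose levels. A level with five or fewer subjects cannot give p < 0.05, and an interval computed within it cannot reach 95% coverage. Both statements are exact and need no assumption about the drug. With 12 subjects, at least two of the four levels are always in that position. Replacement of non-completers (SAP 3.5) could raise the number treated above 12, while missing assessments lower the usable number.

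How much is lost depends on how many subjects escalate. Under the constant-rate, 45-day illustration it is substantial near a spontaneous rate of 6 and slight at 1. Whether the median interval is pooled cannot be settled from the text.

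**What to change.** In SAP 8.3.1 to 8.3.4, state that the inferential analysis for each score is one signed-rank test and one median interval over all subjects, using the last assessment on each subject's own final dose, and that per-level results are descriptive. With 12 non-zero changes the smallest attainable p is 2/4096 = 0.0005. If per-level tests are wanted as well, run them only where a level has at least six subjects with data, as the SAP already requires in 8.2.1, 9.5, 10.4 and 10.5. Say explicitly that the interval follows the same pooling as the test, and align the Appendix I code with it.

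The cost is SAP wording: no new data, visits or subjects. The pooled estimate averages over doses, which the report should say.
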